Safety Monitoring: Because the intervention in this study does not involve any direct contact with subjects, this study is highly unlikely to involve risks to patient. Nonetheless, the PI or anyone else who has contact with study participants during study activities have the responsibility to monitor for any potential adverse events and protocol deviations. Any adverse participant event will be reported immediately to PI [name], who will contact the participant and determine if additional intervention is needed to ensure participant safety. Protocol deviations will also be immediately reported to [name] who will ensure that adverse events deemed to be unanticipated problems and protocol deviations are properly reported to the IRB in a timely manner. Detailed written documentation will be kept for all adverse events that occur over the course of the study. PI [name] holds weekly meetings with his study personnel where they will discuss adverse events and protocol deviations associated with this project and ways to reduce repeat occurrences. Research staff will examine all cumulative adverse events quarterly to determine if there are any systematic problems and to implement protocol corrections as needed after receiving IRB approval.

Data Monitoring: We will use password protected excel documents to store study data, track data screening, enrollment and participation, create surveys, generate reports, and enhance project management. All information linking study data to PHI will be kept within VHA electronically in secure computer files stored behind firewalls requiring password access, or in hardcopy form in locked file cabinets in locked offices. All patient identifiers will be removed prior to analysis. All investigators and team members who will have access to the data will have received appropriate background checks as part of hiring and/or credentialing, and will have completed Data Security Training within the prior 12 months. The project manager will conduct a review of study files every six months to assure compliance with approved procedures. The research team will work closely with the VAPORHCS Information Security Officer and Contracting Officer to ensure that any data transfer, storage, and handling by non-VA entities adhere to VA security policies.

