By examining different types of nudges in different intervention arms, this project will help advance scientific understanding of the mechanisms behind behavior change related to appointment attendance. If successful, it would also lay the groundwork for a subsequent study where we would have the resources to conduct full factorial testing, identify optimal combinations of messages/nudges, and determine whether synergistic effects can be achieved by combining messages. **Table 2** contains a more detailed description of what kinds of messages fall into each of the four categories of nudges. For most of the four concepts, multiple draft messages are presented.

Table 2: Messages included in the appointment reminder based on the related concept

Concept	Message
Caring	We're here for you.
Consequences for Others	Call now so we can help another Veteran in need.
Consequences for Self	Attending appointments lowers your chances of being hospitalized.
Consequences for Self	If you miss your appointment, you may have to wait a while to be seen.
Social Norms	Most Veterans make a point to attend their VA appointments. If they can't make their appointments, most Veterans also make an effort to let us know.
Behavioral Instructions	Need to change or cancel your appointment? Take these 2 simple steps today: 1) Call the clinic at [contact]. 2) Give your name, last 4, and appointment information. It's fine to leave a message.

Intervention 1 (Social Norms + Behavioral Instructions): A letter with two types of nudges. One points out the common behavior of attending appointments. And one provides clear, specific instructions for making appointment changes. The appointment reminder also includes usual care (basic appointment information on date, location, and phone number(s) for scheduling changes).

Research has shown that social norms messages have a positive impact on behavioral action, however it is not clear how effective it is in comparison to messages framed around consequences. Additionally, we did not use the caring message in this intervention arm to allow for comparison of whether the caring message on its own has a positive impact.

Intervention 2 (Caring + Consequences for Others + Behavioral Instructions): A letter with three types of nudges. One suggests that the institution cares about the patient. One highlights a potential negative consequence for others if the patient no-shows. And one provides clear, specific instructions for making appointment changes.

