The appointment reminder also includes usual care (basic appointment information on date, location, and phone number(s) for scheduling changes).

During the development of the conceptual messages the gain framed consequences for others message and the caring message both received favorable responses, and participants often put these messages together. These messages emphasize a personal connection between the recipient of the letter, the clinic, and other patients at the clinic. This positive message and personal connection calls upon a sense of social responsibility, which we anticipate will have a positive impact on no-show rates.

Intervention 3 (Caring + Consequences for Self + Behavioral Instructions): A letter with three types of nudges. One suggests that the institution cares about the patients. One highlights potential negative consequences for the patient if s/he no-shows. And one provides clear, specific instructions for making appointment changes. The appointment reminder also includes usual care (basic appointment information on date, location, and phone number(s) for scheduling changes).

On their own, each consequences-for-self message had mixed reactions. By including both messages we hope that if one concept does not appeal to a participant, that the second will. By including the caring message, we are conveying the idea that the reminder of the consequences if they no-show is coming from a place of caring for the recipient of the letter, and thus whether framed as a personal gain or loss the recipient may be more open to hearing the consequences-for-self messages and be gently nudged to action.

Intervention 4 (Caring + Consequences for Others + Consequences for Self + Social Norms + Behavioral Instructions): A letter with all four types of nudges combined. One suggests that the institution cares about the patients. One highlights a potential negative consequence for others if the patient no-shows. One highlights potential negative consequences for the patient if s/he no-shows. One points out the common behavior of attending appointments. And one provides clear, specific instructions for making appointment changes. The appointment reminder also includes usual care (basic appointment information on date, location, and phone number(s) for scheduling changes).

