While we anticipate that each intervention arm will have an impact on No-Show rates, it is not clear which messaging combination will have the greatest impact. While we combine some messages, we also anticipate that combining more messages will not have an additive effect. Instead, too many messages may dilute the effectiveness of all the messages. To test this, we developed this intervention arm to include every

message, to determine if behavioral nudges are best used in shorter and smaller combinations.

H. Procedure: Because VHA appointments are managed in the Veterans Health Information Systems and Technology Architecture (VistA) and related data systems, letters and postcards will be designed and formatted within the constraints of VistA and related system requirements. The research team will work with and support clinical application coordinators in mental health and primary care to modify, audit, and maintain letter template changes. Our research team is experienced with staffing resources and procedures necessary in preparing large and customized patient mailings⁸⁵. Because letter templates are unique to each provider and his/her associated clinic(s), the research team will take advantage of this specificity when tailoring messages. Intervention content will be applied to pre-appointment reminder letters and/or postcards, which in VAPORHCS are mailed at the time of scheduling. (Our preliminary data shows that, as of July 2016, in VAPORHCS, appointments are scheduled, on average, 22-33 days before the appointment in primary care and mental health.) In addition, intervention content will also be adapted to no-show letters and/or postcards, which are sent after a no-show, to help reduce risk of repeated no-shows.

I. Measures:

Outcomes for Aim 2
(Determine the effect of four versions of enhanced appointment reminders on measures relevant to treatment access, compared with usual reminders) **and Aim 3** (Evaluate differences in treatment effect associated with four versions of enhanced appointment reminders): **Table 3** summarizes the outcomes used in these Aims.

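### The five arms do not provide the comparison of the caring message that the protocol gives as its reason for leaving caring out of Intervention 1, and the omission also prevents social norms from being separated from consequences

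*Combined protocol and SAP*

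**What the plan says.** Section G (Study Groups and Intervention Description) defines five equally allocated groups:

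- Intervention 1: social norms + behavioral instructions
- Intervention 2: caring + consequences for others + behavioral instructions
- Intervention 3: caring + consequences for self + behavioral instructions
- Intervention 4: all five of these nudges
- Usual care: none

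All four active letters also use salience formatting such as selective bolding.

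Under Intervention 1 the protocol says of social norms messages: "however it is not clear how effective it is in comparison to messages framed around consequences". Its next sentence explains that caring was omitted from this arm "to allow for comparison of whether the caring message on its own has a positive impact". Earlier in the section the arms are given a wider purpose: "By examining different types of nudges in different intervention arms, this project will help advance scientific understanding of the mechanisms".

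The Aim 3 hypothesis, in the list of aims and again in Section J (Data Analysis), first says that effects will vary by arm. It then adds that some types, or categories, of nudge will have larger proportional effects than others. Section J plans only pairwise tests: each letter against usual care (Aim 2) and each letter against each other letter (Aim 3).

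**The concern.** The caring sentence describes a comparison that can be looked for directly in the arm definitions, and it is not there. Leaving caring out of Intervention 1 alone also makes that arm differ from Interventions 2 and 3 in two respects at once: norms replace a consequences nudge, and caring is absent.

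What is at stake is how Aim 3 is reported. If Intervention 2 or 3 does better than Intervention 1, the nudge-type clause of the hypothesis invites the statement that consequences messages outperform social norms. A single sentence of caring text could account for the gap. The results are meant to inform a later factorial study and wider implementation, so a wrong attribution would carry forward.

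**Working it through.** The plan states no figure on this point. The check is whether the arm definitions in Section G contain the contrast claimed.

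**Step 1: all 10 arm pairs.** Write N = norms, B = instructions (together with the salience formatting, which appears in exactly the same arms), C = caring, O = others, S = self. Under additive effects, the case most favorable to the protocol's sentence:

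| Pair | Difference |
|---|---|
| I1 − usual care | N + B |
| I2 − usual care | B + C + O |
| I3 − usual care | B + C + S |
| I4 − usual care | N + B + C + O + S |
| I2 − I1 | C + O − N |
| I3 − I1 | C + S − N |
| I4 − I1 | C + O + S |
| I3 − I2 | S − O |
| I4 − I2 | N + S |
| I4 − I3 | N + O |

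C appears in six rows and alone in none. Neither N − O nor N − S appears.

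**Step 2: can arms be combined to recover caring?** Take the shift N −0.5, B +0.5, C −1, O +0.5, S +0.5 and add it up in each arm:

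- I1: −0.5 + 0.5 = 0
- I2: 0.5 − 1 + 0.5 = 0
- I3: 0.5 − 1 + 0.5 = 0
- I4: −0.5 + 0.5 − 1 + 0.5 + 0.5 = 0
- Usual care: 0

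Any multiple of this shift leaves all five arm means unchanged while moving every single-nudge effect. The arm-by-nudge matrix therefore has rank 4 for 5 nudge effects. None of the five effects is estimable. N − O changes by −0.5 − 0.5 = −1 under the shift, and so does N − S, so neither is estimable. O − S changes by 0.5 − 0.5 = 0 and is estimable, as I2 − I3.

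**Step 3: illustration.** The effects below are assumed, in percentage points of no-show reduction. Only the 0.6 is borrowed, from the pilot effectiveness study.

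| | N | B | C | O | S | I1 | I2 | I3 | I4 |
|---|---|---|---|---|---|---|---|---|---|
| Set A | 1.0 | 0.5 | 0.6 | 1.0 | 1.0 | 1.5 | 2.1 | 2.1 | 4.1 |
| Set B | 0.7 | 0.8 | 0 | 1.3 | 1.3 | 1.5 | 2.1 | 2.1 | 4.1 |

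Set B is Set A plus 0.6 times the shift. In A, norms equal consequences and caring explains the whole I2 − I1 gap of 0.6. In B, caring does nothing and each consequences nudge is nearly twice norms (1.3/0.7 = 1.86). The two sets give identical arm results.

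**Step 4: the nearest available contrast.** I1 + I2 + I3 − I4 − 2 × usual care = (N + B) + (B + C + O) + (B + C + S) − (N + B + C + O + S) = C + 2B. It equals caring only if effects are additive and B = 0. With equal arm variances its squared weights sum to 1 + 1 + 1 + 1 + 4 = 8, against 2 for a simple pair. Its standard error is therefore √(8/2) = 2 times that of a pairwise comparison. Section J does not plan it.

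**Step 5: is the omission the cause?** As a check only, put caring into Intervention 1 as well. Then I1 − I2 = N − O and I1 − I3 = N − S, both clean under additivity. Caring would then appear in exactly the same arms as instructions and would still not be identified. So the omission costs the norms-versus-consequences comparison and does not gain the caring one.

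**The case against.** The best defense is that no planned test claims to estimate caring. Section J compares whole letters, Aim 3 is framed around four versions of the reminder, and its hypothesis begins with variation by arm. Sections G and L leave factorial testing to later work for reasons of power. All of this is correct, and it is why the analysis itself is sound. But none of it withdraws the caring sentence or the nudge-type clause of the Aim 3 hypothesis.

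The sentence could be read loosely, as letters with caring against the letter without. That does not help: Intervention 1 is the only active letter without caring, and it differs from each of the others in consequences content too.

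The worked example uses additive effects and gives Intervention 4 a reduction of 4.1 points, larger than the 1.9% and 2.7% in the power section. The size is immaterial, because the shift in step 2 works at any scale. Additivity is the lenient assumption, since the protocol says "we also anticipate that combining more messages will not have an additive effect".

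A reader might go further and infer that no result of this trial can bear on caring. The documents do not support that. Under additivity, and if instructions and formatting do no harm, C + 2B is an upper bound on caring's benefit, though an unplanned and imprecise one. A reader might also infer that the protocol is undecided on whether caring is a nudge type. Section G's overview lists it explicitly among five, and the descriptions of Interventions 2 and 3 count it. The phrase "A letter with all four types of nudges combined", followed by five items, is an editorial slip. Nor should the background remarks on knowledge gaps be taken as a stated trial goal.

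**Conclusion.** The stated purpose of omitting caring from Intervention 1 is not met by the design. None of the 10 arm pairs isolates caring. Under additivity it is not point-identified without the further assumption that instructions and salience formatting have zero effect. The protocol makes neither assumption: it expects non-additivity, and its background presents clear instructions as effective. Interventions 1 versus 2 and 1 versus 3 likewise do not separate norms from consequences.

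Intervention 2 versus 3 is the one contrast that isolates a difference between two nudge types, but it should be read narrowly. Both letters carry caring, and the protocol expects caring to change how the self messages are received: "whether framed as a personal gain or loss the recipient may be more open to hearing the consequences-for-self messages". The comparison is therefore others versus self in letters that also contain caring and instructions. The letters differ in message count (one others message, two self messages) and in framing. The others message is gain framed: "the gain framed consequences for others message and the caring message both received favorable responses". The self messages mix gain and loss.

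Severity is low. Aim 2, the letter-against-letter tests and the question of whether Intervention 4 dilutes the messages all stand. Only the wording and the interpretation of Aim 3 are affected.

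**What to change.** 1. Section G, Intervention 1: delete the caring sentence, or replace it with a statement that the design does not estimate the effect of caring separately.
2. Aim 3 hypothesis, in the list of aims and in Section J: replace the clause about types or categories of nudges with a difference in effect among the four letters.
3. Section J: state that Intervention 1 versus 2 and Intervention 1 versus 3 will not be attributed to norms versus consequences.
4. Section J: state that Intervention 2 versus 3 will be interpreted only as others versus self messages within letters that also carry caring and instructions, and note the differences in message count and framing.
5. Editorial: in Section G, change the references to four nudge types (the text introducing Table 2 and the Intervention 4 description) to agree with the five in the overview and tables.

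The cost is wording only. Letters, randomization, sample size, model and planned tests stay as they are. What is given up is any claim from Aim 3 about caring, or about norms against consequences, which the data could not have supported without the extra assumptions above.

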Our primary outcome will be no-show rate, or the proportion of total appointments that are classified as a no-show, relative to the total number of appointments scheduled. The numerator (“no-shows”) consists of appointments marked as a no-show and appointments canceled by the patient or clinic after the appointment time. The denominator (“total appointments”) consists of no-shows and completed appointments. No-show rates will be measured at the provider-level.

Table 3. Trial Outcomes (Aims 2 & 3)

Outcome	Measure	Data Source
Primary	No-show rate	CDW
Secondary	Cancellation rate	CDW
	Advance cancellation rate	CDW
	Patient-initiated cancellation rate	CDW
Exploratory	Raw wait time	CDW
	Clinically indicated wait time	CDW
	Waiting room time	SHEP
	New mental health appointment wait time	CDW

Our secondary outcome will be cancellation rate, defined as the proportion of scheduled appointments that are marked as canceled. In addition to overall cancellation rate, we will also determine the rate amongst the subset of cancellations that are advance cancellations and patient-initiated cancellations. Advance cancellations, defined here as at least five days before appointment, provide a metric with a reasonable window of time (informed by preliminary data provided by our schedulers) that allows the opportunity to fill a cancelled slot with another waiting Veteran. Patient-initiated cancellations provide a more specific indication of intervention effects on cancellation behavior. Cancellation rates will be measured at the provider-level.

Finally, as exploratory outcomes, we will calculate wait time and number of unique patients seen per day. The latter is simply the number of daily completed encounters, adjusting for patients who have multiple encounters in the same day. For wait time, we will use multiple validated metrics:

- Raw wait time is defined as the length of time in days between the date an appointment was created and the date the appointment was completed⁷⁴. If an appointment is cancelled or a no-show, the wait time will be calculated based on the next appointment that is scheduled and completed in the same clinic stop code.

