effectiveness of interventions varies. For example, we will explore whether the effect of the interventions differ between men and women. To analyze our exploratory outcomes on appointment wait time, we will evaluate time-to-completed appointment using an extended multivariate Cox regression model to account for multiple appointments at the patient level and clustering at the provider level.

Aim 2 Hypotheses: To address Hypothesis 1 (Each intervention group will have a lower no-show rate, as compared with usual care) and Hypothesis 2 (Each intervention group will have a higher cancellation rate, as compared with usual care), we will conduct pairwise comparisons to test for differences between the interventions and usual care as $H_0: \beta_j=0$ for Interventions $j=1,2,3,4$.

Aim 3 Hypothesis (Effect size of nudges will vary by intervention arm such that some categories of nudges have a larger proportional effect than others): We will conduct pairwise comparisons of no-show and cancellation rates by testing the linear combinations between each of the four intervention arms (e.g., Intervention 1 and Intervention 2; $H_0: \beta_1=\beta_2$).

Aim 4: ATLAS.ti software will be used for data management. We will employ a “rapid assessment process,” which is useful for quickly developing understanding from an insider’s perspective and informing future implementation efforts^{81,92}. This multi-step process will be as follows: 1) create domain names for each interview question; 2) create and test a summary template; 3) summarize interview transcripts using the summary template, and 4) transfer summaries into a matrix (respondent x domain) data display⁹³. Our summary template will consist of domains and constructs from our interview guides (i.e., CFIR), and we will compose a templated summary for each interview. We will review these summaries on a regular basis (approximately every five interviews) to ensure interviews build iteratively on emergent findings.

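### Hypothesis 2 is stated on advance cancellations but tested on all cancellations, and no outcome combines no-shows with short-notice cancellations, so a shift from one to the other would favour both tests

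*Combined protocol and SAP*

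**What the plan says.** **Primary outcome (section I, Measures).** The numerator of the no-show rate "consists of appointments marked as a no-show and appointments canceled by the patient or clinic after the appointment time". The denominator "consists of no-shows and completed appointments", although the sentence introducing the outcome describes the rate as "relative to the total number of appointments scheduled".

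**Cancellation outcomes (section I).** The overall cancellation rate is "defined as the proportion of scheduled appointments that are marked as canceled", with no limit on timing. Table 3 also lists advance and patient-initiated cancellation rates as secondary outcomes. "Advance cancellations, defined here as at least five days before appointment" are singled out because that notice gives a window "that allows the opportunity to fill a cancelled slot with another waiting Veteran". The text describes these two as rates within the subset of cancellations, so their denominator is unclear.

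**Hypothesis 2.** The Aims at the front of the protocol state it on advanced cancellations. Section J (Aim 2 Hypotheses) gives the version to be tested: "Each intervention group will have a higher cancellation rate, as compared with usual care".

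**Other relevant outcome.** The number of unique patients seen per day is exploratory. It appears in the text of section I but not in Table 3, and section J sets out no analysis for it.

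**The concern.** Aim 2 concerns access, and the plan's reason for the five-day definition is that notice lets another Veteran use the slot. The primary outcome, however, does not distinguish a no-show that became an attended visit from one that became a call an hour beforehand. Both leave the numerator, and the second also leaves the denominator. The version of Hypothesis 2 in section J then credits the late call as a benefit. Only the version in the Aims separates cancellations inside the refill window from late ones, and section J does not carry it forward.

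The plan expects some substitution. The Background says reminders may lead patients to cancel instead of not appearing, and all four letters carry the instruction that makes cancelling easier, including that it is "fine to leave a message". The Significance section also reads averted no-shows directly as completed visits. At stake is the access interpretation of Aim 2, not the validity of the comparison of no-show rates.

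**Working it through.** **The plan's own figures.** The Significance section says a one percent reduction in no-shows would yield 90,000 more completed visits a year. This reproduces from the nine million no-shows in the Background: 0.01 × 9,000,000 = 90,000. It counts each averted no-show as one completed visit.

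The stated 80% power for 2.7 points in mental health (section K) cannot be reproduced exactly, because the simulation inputs are not given. A clustered two-proportion approximation used two-sided alpha 0.05 (assumed), 275/5 = 55 providers per arm, 102,060/275 = 371 appointments each, baseline 12% to 18% and rho 0.02 to 0.05. It gives 64% to 99.8% with rho on the logistic scale, and 38% to 86% with a design effect. The stated value lies inside both ranges, and this point does not depend on it.

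**Inputs for the shift scenario.**
- Baseline no-show rate p0 = 13.5%, the middle of the 13–14% in the Background. The local rates are not given, so 8% to 18% is an assumed range.
- Share of scheduled appointments cancelled: 25%, range 15% to 35%. This is assumed, as the documents give no cancellation rate.
- Half of those cancellations are at least five days ahead (assumed).
- Target rate t = 13.5% − 2.7% = 10.8%, using the design effect in section K.

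**Method.** Take 1,000 scheduled appointments with N no-shows, C completed and K cancelled. Move s no-shows to cancellations zero to four days ahead, holding C and advance cancellations fixed. Setting (N − s)/(N − s + C) = t gives s = N − C·t/(1 − t).

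**Central case.** K = 250, N = 0.135 × 750 = 101.25, C = 648.75.
s = 101.25 − 648.75 × 0.108/0.892 = 22.7, which is 22.7/101.25 = 22.4% of no-shows.

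| Measure | Before | After |
|---|---|---|
| No-show rate, no-shows + completed | 13.5% | 78.55/727.3 = 10.8% |
| No-show rate, all scheduled | 10.1% | 7.9% |
| Overall cancellation rate | 25.0% | 27.3% |
| Completed visits per 1,000 | 648.75 | 648.75 |
| Advance cancellations, of scheduled | 12.5% | 12.5% |
| Advance cancellations, of cancellations | 50% | 125/272.7 = 45.8% |
| No-shows + cancellations under five days, of scheduled | 22.6% | 22.6% |

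The last row includes late cancellations by either party. Limiting it to patient-initiated ones lowers the level but still leaves no change.

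**Ranges.** The share that must shift is s/N = 1 − [t/(1 − t)]/[p0/(1 − p0)], which does not depend on the cancellation rate. For 2.7 points it is 35.6% at p0 = 8% and 17.7% at p0 = 18%. For 1.9 points it is 25.3%, 15.9% and 12.6% at 8%, 13.5% and 18%. For 2.7 points the overall cancellation rate rises by 1.9 to 2.7 points across the grid.

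**Reading across.** Hypothesis 1 and the section J version of Hypothesis 2 both move in the favourable direction. The Aims version shows no gain: it is flat over scheduled appointments and lower over cancellations. Using all scheduled appointments as the no-show denominator does not remove the effect.

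**The case against.** **The five-day figure is not a definition of loss.** A reader might infer that the plan itself treats a cancellation under five days ahead as a lost slot, equal to a no-show. It does not. It calls five days a reasonable window giving an opportunity to refill, and does not say that shorter notice wastes the slot. This objection stands, so the scenario shows only that no cancellation is added inside that window.

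**The shift would not be invisible.** A reader might also infer that late cancelling would simply be reported as better access. Advance cancellation rate is a listed secondary outcome, section J applies the mixed model to the cancellation rates, and patients seen per day would stay flat if nothing was refilled. This stands in part. The denominator for advance cancellations is unclear and patients seen per day is exploratory. Overall minus advance cancellations mixes in clinic cancellations and, as worded, cancellations after the appointment time that are already counted as no-shows. No rule says how discordant results are read.

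**The letters prompt early calls.** Table 2 asks for the steps to be taken the same day, and section H says letters are mailed at scheduling, on average 22 to 33 days ahead. The pilot reported no-shows down 0.6% and attendance up 3.8%. If both are over all scheduled appointments, which is not stated, cancellations fell by 3.8 − 0.6 = 3.2 points. This makes a large late shift less likely but does not exclude one.

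**The scenario is an extreme.** It turns every averted no-show into a late cancellation and rests on assumed cancellation rates. That is true: it shows what the outcomes could fail to separate, and is not a forecast.

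**Conclusion.** The point holds as an inconsistency in Hypothesis 2 together with a gap in the outcome set. The Aims and section J name different measures, and the tested one gives credit whatever the notice. No listed outcome adds no-shows and short-notice cancellations. Under section J, a shift of about 22% of no-shows (18% to 36%) would produce the full 2.7-point effect and raise overall cancellations by about 2.3 points (1.9 to 2.7), with completed visits and advance cancellations unchanged. These figures rest on an assumed baseline of 8% to 18%, an assumed cancellation rate of 15% to 35%, and the assumption that all averted no-shows become late cancellations. The documents do not allow the actual shift to be estimated.

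The documents do not support a claim that the no-show comparison is invalid or that a false access finding is to be expected. This is a cheap improvement to the secondary outcomes, and the primary outcome need not change.

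**What to change.** 1. Reconcile the Aims with section J. Test Hypothesis 2 on advance cancellations (at least five days ahead) over all eligible scheduled appointments, and keep the overall cancellation rate as a supporting outcome.
2. Add one secondary or sensitivity outcome to Table 3: (no-shows + patient-initiated cancellations made fewer than five days before the visit) / all eligible scheduled appointments, each appointment counted once. Analyse it with the same mixed logistic model, per letter and per specialty, and report it beside the no-show rate when access is discussed.
3. Leave the primary outcome as it is. Do not require the composite to fall before an access statement can be made, because it has no power calculation and should not override the powered outcome.

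**Cost.** One more model per specialty. Appointment status, cancellation timing and initiator are already needed for Table 3. It adds one unpowered comparison per letter in each specialty, and late-cancelled slots that were in fact refilled will be counted as lost, which the report should say.
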